Adverse event

An adverse event (AE) is defined as any untoward medical occurrence, including an exacerbation of a pre-existing condition, in a patient in a clinical investigation who received a pharmaceutical product. The event does not necessarily have to have a causal relationship with this treatment.

Serious adverse event

A serious adverse event (SAE) is defined as any AE which results in death, is immediately life-threatening, results in persistent or significant disability / incapacity, requires or prolongs patient hospitalisation, is a congenital anomaly / birth defect, or is to be deemed serious for any other reason if it is an important medical event when based upon appropriate medical judgement which may jeopardise the patient and may require medical or surgical intervention to prevent one of the other outcomes listed in the above definitions.

Patients may be hospitalised for administrative or social reasons during the study (e.g. days on which infusion takes place, long distance from home to site,). These and other hospitalisations planned at the beginning of the study do not need to be reported as a SAE in case they have been reported at screening visit in the source data and have been performed as planned.

Adverse Events of Special Interest

Based on regulatory recommendation that is based on the experience with other compounds in the DPP-4 inhibitor class, the following events should be defined as adverse events of special interest.

- Hypersensitivity reactions such as angioedema, angioedema-like events, and anaphylaxis
- Skin lesions such as exfoliative dermatitis, and exfoliative rash
- Renal adverse events (e.g. renal failure, $\geq 2x$ increase of creatinine from baseline)
- Pancreatitis

Hepatic adverse events such as hepatitis, liver injury, and increased liver enzymes. Hepatic injury is defined by the following alterations of liver parameters: For patients with normal liver function (ALT, AST and bilirubin within normal limits) at baseline an elevation of AST and/or ALT >3 fold ULN combined with an elevation of bilirubin >2 fold ULN measured in the same blood draw sample.

Refer to the appendix 1 for a list of preferred terms (PT's) that are considered as AEs of Special Interest.

Protocol-specified significant events are to be reported in an expedited manner similar to Serious Adverse Events, even if they do not meet any of the seriousness criteria.

Intensity of adverse event

The intensity of the AE should be judged based on the following:

- Mild: Awareness of sign(s) or symptom(s) which is/are easily tolerated
- Moderate: Enough discomfort to cause interference with usual activity
- Severe: Incapacitating or causing inability to work or to perform usual activities

Causal relationship of adverse event

Medical judgment should be used to determine the relationship, considering all relevant factors, including pattern of reaction, temporal relationship, de-challenge or re-challenge, confounding factors such as concomitant medication, concomitant diseases and relevant history. Assessment of causal relationship should be recorded in the case report forms.

Yes: There is a reasonable causal relationship between the investigational product administered and the AE.

No: There is no reasonable causal relationship between the investigational product administered and the AE.

Worsening of the underlying disease or other pre-existing conditions

Worsening of the underlying disease or of other pre-existing conditions will be recorded as an (S)AE in the (e)CRF.

Changes in vital signs, ECG, physical examination, and laboratory test results

Changes in vital signs, ECG, physical examination and laboratory test results will be recorded as an (S)AE in the (e)CRF , if they are judged clinically relevant by the investigator.

Responsibilities for SAE reporting

The Sponsor shall report (i.e., from signing the informed consent onwards through the trialdefined follow-up period) all SAEs and non-serious AEs occurring at the same time and/or which are medically related to the SAE and Adverse Events of Special Interest by fax or other secure method to the BI Unique Entry Point in accordance with timeline specified in the pharmcovigilance agreement

For each adverse event, the investigator will provide the onset date, end date, intensity, treatment required, outcome, seriousness, and action taken with the investigational drug. The investigator will determine the expectedness of the investigational drug to the AEs as defined in the Listed Adverse Events section of the Boehringer Ingelheim's (BI's) Investigator Brochure for the Product or BI Drug Information e.g. Summary of Product Characteristics (SmPC) or Product Information (PI) for the authorised Study Drug provided by BI.

Appendix 1

Following preferred terms are considered as Adverse Event of Special Interest

Hepatic events

Acute graft versus host disease in liver
Acute hepatic failure
Alanine aminotransferase abnormal
Alanine aminotransferase increased
Ammonia abnormal
Ammonia increased
Ascites
Ascites
Aspartate aminotransferase abnormal
Aspartate aminotransferase increased
Asterixis
Autoimmune hepatitis
Bacterascites
Bacterascites
Bile output abnormal
Bile output decreased
Biliary cirrhosis
Biliary cirrhosis primary
Biliary fibrosis
Bilirubin conjugated abnormal
Bilirubin conjugated increased
Bilirubin excretion disorder
Biopsy liver abnormal
Blood bilirubin abnormal
Blood bilirubin increased
Blood bilirubin unconjugated increased
Caput medusae
Child-Pugh-Turcotte score increased
Cholaemia
Cholestasis
Cholestatic liver injury
Cholestatic liver injury
Cholestatic pruritus
Chronic hepatic failure
Chronic hepatitis
Coma hepatic
Cryptogenic cirrhosis
Cytolytic hepatitis
Duodenal varices
Foetor hepaticus
Galactose elimination capacity test abnormal

Galactose elimination capacity test decreased
Gamma-glutamyltransferase abnormal
Gamma-glutamyltransferase increased
Gastric varices
Gastric varices haemorrhage
Guanase increased
Hepaplastin abnormal
Hepaplastin decreased
Hepatectomy
Hepatic artery flow decreased
Hepatic atrophy
Hepatic calcification
Hepatic cirrhosis
Hepatic congestion
Hepatic encephalopathy
Hepatic encephalopathy prophylaxis
Hepatic enzyme abnormal
Hepatic enzyme decreased
Hepatic enzyme increased
Hepatic failure
Hepatic fibrosis
Hepatic function abnormal
Hepatic hydrothorax
Hepatic hydrothorax
Hepatic infiltration eosinophilic
Hepatic lesion
Hepatic mass
Hepatic necrosis
Hepatic pain
Hepatic sequestration
Hepatic steatosis
Hepatic vascular resistance increased
Hepatitis
Hepatitis acute
Hepatitis cholestatic
Hepatitis cholestatic
Hepatitis chronic active
Hepatitis chronic persistent
Hepatitis fulminant
Hepatitis fulminant
Hepatitis toxic
Hepatobiliary disease
Hepatobiliary scan abnormal
Hepatocellular foamy cell syndrome
Hepatocellular injury
Hepatomegaly

Hepatopulmonary syndrome
Hepatorenal failure
Hepatorenal syndrome
Hepatosplenomegaly
Hepatotoxicity
Hyperammonaemia
Hyperbilirubinaemia
Hyperbilirubinaemia
Hypercholia
Hypertransaminasaemia
Icterus index increased
Ischaemic hepatitis
Jaundice
Jaundice cholestatic
Jaundice hepatocellular
Kayser-Fleischer ring
Liver and small intestine transplant
Liver disorder
Liver function test abnormal
Liver induration
Liver injury
Liver operation
Liver palpable subcostal
Liver scan abnormal
Liver tenderness
Liver transplant
Lupoid hepatic cirrhosis
Lupus hepatitis
Mitochondrial aspartate aminotransferase increased
Mixed liver injury
Mixed liver injury
Molar ratio of total branched-chain amino acid to tyrosine
Nodular regenerative hyperplasia
Ocular icterus
Oedema due to hepatic disease
Oedema due to hepatic disease
Oesophageal varices haemorrhage
Perihepatic discomfort
Portal hypertension
Portal hypertensive enteropathy
Portal hypertensive gastropathy
Portal triaditis
Portopulmonary hypertension
Radiation hepatitis
Renal and liver transplant
Retrograde portal vein flow

Retrograde portal vein flow
Reye's syndrome
Subacute hepatic failure
Total bile acids increased
Transaminases abnormal
Transaminases increased
Ultrasound liver abnormal
Urine bilirubin increased
Urobilin urine present
Varices oesophageal
X-ray hepatobiliary abnormal

Following preferred terms are considered as Adverse Event of Special Interest

Hypersensitivity reactions

Allergic bronchitis
Allergic cough
Allergic oedema
Allergic respiratory disease
Allergic respiratory symptom
Alveolitis allergic
Anaphylactic reaction
Anaphylactic shock
Anaphylactic transfusion reaction
Anaphylactoid reaction
Anaphylactoid shock
Angioedema
Bronchial hyperreactivity
Bronchospasm
Circulatory collapse
Circumoral oedema
Conjunctival oedema
Corneal oedema
Cough
Drug eruption
Drug hypersensitivity
Epiglottic oedema
Erythema
Eye oedema
Eye swelling
Eyelid oedema
Face oedema
First use syndrome
Gingival oedema

Gingival swelling
Gleich's syndrome
Hereditary angioedema
Hypersensitivity
Idiopathic urticaria
Kounis syndrome
Laryngeal oedema
Laryngotracheal oedema
Lip oedema
Lip swelling
Oculorespiratory syndrome
Oedema mouth
Oropharyngeal swelling
Palatal oedema
Periorbital oedema
Pharyngeal oedema
Pruritus
Pruritus allergic
Pruritus generalised
Rash
Rash erythematous
Rash generalised
Rash pruritic
Scleral oedema
Shock
Small bowel angioedema
Swelling face
Swollen tongue
Tongue oedema
Toxic skin eruption
Tracheal oedema
Type I hypersensitivity
Type I hypersensitivity
Urticaria
Urticaria
Urticaria cholinergic
Urticaria chronic
Urticaria papular
Urticaria papular
Wheezing

**Following preferred terms are considered as
Adverse Event of Special Interest**

Pancreatitis

Cullen's sign

Hereditary pancreatitis
Ischaemic pancreatitis
Oedematous pancreatitis
Pancreatic abscess
Pancreatic necrosis
Pancreatic phlegmon
Pancreatic pseudocyst
Pancreatic pseudocyst drainage
Pancreatitis
Pancreatitis acute
Pancreatitis chronic
Pancreatic haemorrhage
Pancreatitis haemorrhagic

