Aim 3.2: To compare the endogenous glucose output and suppression of endogenous glucose production by insulin during HE clamp prior to and following 12 weeks of linagliptin or placebo.

Aim 3.3: To compare mRNA and protein expression of SOCS-3 and PTP-1B, two important insulin resistance inducers, in MNC and adipose tissue prior to and following 12 weeks of linagliptin or placebo.

Hypothesis 4: Linagliptin increases post-prandial GLP-1, GIP and c-peptide concentrations.

Aim 4.1: To measure GLP-1, GIP and c-peptide concentrations following HFHC meal prior to and following 12 weeks of linagliptin or placebo.

RESEARCH DESIGN AND METHODS

RESEARCH DESIGN:

This is a prospective, **randomized, placebo -controlled, double blind** trial. The study will be conducted at the Diabetes – Endocrinology Center of Western New York under the direction of [name], M.D.

STUDY POPULATION:

Forty type 2 diabetic patients in the age group of 20 – 80 years will be recruited into the study. An informed consent will be obtained. They will be randomized into 2 groups: placebo and 5 mg/day linagliptin for 12 weeks

INCLUSION CRITERIA:

- Age 20-80 years inclusive.
- Type 2 diabetes
- $BMI \geq 30 \text{ kg/m}^2$
- Subjects on statins, ACE inhibitors, thiazolidinediones and antioxidants will be allowed as long as they are on stable doses of these compounds and the dosage is not changed during the course of study.
- $\text{HbA1c} \leq 7.5\%$

EXCLUSION CRITERIA:

- Use of GLP-1 agonists or DPP-IV therapy in the last 3 months.
- History of Pancreatitis.
- Risk for pancreatitis, i.e., history of gallstones, alcohol abuse, and hypertriglyceridemia.
- Subjects who are taking antiplatelet or anticoagulant medications will be excluded from the fat biopsy portion of the study.
- Coronary event or procedure (myocardial infarction, unstable angina, coronary artery bypass, surgery or coronary angioplasty) in the previous four weeks
- Hepatic disease (liver function tests more than 3 times the upper limit of normal)
- Renal impairment (serum eGFR <30 ml/min)
- Any other life-threatening, non-cardiac disease
- Uncontrolled hypertension (BP > 160/100 mm of Hg)
- Congestive Heart Failure class III or IV.
- Use of an investigational agent or therapeutic regimen within 30 days of study

- Participation in any other concurrent clinical trial

STUDY DESIGN:

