This study requires 8 visits to the clinic: a screening visit (week -1), a baseline visits (weeks 0, 1 and 2) and then follow up at 2, 4 and 12 weeks after starting the drug. Each visit will consist of blood draw. Subjects will be required to bring in a 24 hour urine sample on weeks 0, 4 and 12.

After the screening visit, subjects will be randomized into 2 groups. The first group will be started on 5 mg linagliptin (supplied by Boehringer Ingelheim Pharmaceuticals, Inc. (BIPI)) daily for 12 weeks. Fructosamine testing will be done at baseline, 4 and 12 weeks (and HbA1c at 0 and 12 weeks) to assess glycemic control. The second group will serve as a control group and will be placed on a placebo (mainly mannitol and corn starch, provided by BIPI in similar shape and color as the active drug) for 12 weeks. Blood samples will be obtained as described for patients on linagliptin. Each blood draw will consist of 45 ml of which 35 ml is collected in EDTA tubes and 10 ml in no-additive tubes. A single dose effect will be investigated at the first day of drug or placebo in 24 subjects (12 from each group) only and blood will be collected at 2, 4 and 6 hr following the first dose. The effect of a standard high-fat high-carbohydrate meal (HFHC) will be investigated on those 12 subjects from each group at baseline and at 12 weeks.

[figure not shown]

Figure 1: Study Design.

STUDY PROCEDURES BY VISIT:

Screening Day

Each subject will complete the following procedures and meet the inclusion and exclusion criteria prior to participating in the study.

1. Medical History
2. Physical Exam
3. Informed consent
4. Baseline lab draws to measure CBC, SMA, lipid profile, fructosamine and HbA1C

Visit 1: Week -2 to Week 0

Visit 1A: The participants will undergo HE clamp. They will be advised to bring 24 hour urine at this visit and research blood will be collected. All patients will have visit A. Visits B and C will be done only in 24 patients (12 in drug group and 12 in placebo group).

Visit 1B: The effect of a standard high-fat high- carbohydrate meal (HFHC) will be investigated in 24 subjects. Fat biopsy will be done before and after the meal.

Visit 1C (in 24 subjects): A single dose (5 mg or placebo) effect will be studied in 24 subjects with blood collections at 2, 4 and 6 hr following the first dose.

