Visits A, B and C will be separated by one week each. All patients will be randomized to drug or placebo groups on visit 1A but only patients who are not participating in visit 1B and 1C will start the drug or placebo at the end of visit 1A (considered week 0). Patients who are participating in visits 1B and 1C will start the drug or placebo at the beginning of visit 1C (considered week 0). Patient will return 2 weeks after starting drug or placebo. The drug will be started after these visits have been completed. Patient will return after 2 weeks.

Visit 2: Week 2

The participants will have their finger stick blood glucose records reviewed and blood will be drawn for labs. A container for 24 hour urine collection will be given. They will be advised to start collecting urine 24 hours prior to their next visit.

Visit 3: Week 4

The participants will have their finger stick blood glucose records reviewed and blood will be drawn for labs. 24 hour urine will be collected. They will be advised to start collecting urine 24 hours prior to their next visit.

Visit 4: Week 12

Visit 4A: The participants will have their finger stick blood glucose records reviewed. They will be advised to bring 24 hour urine at this visit and research blood will be collected. The participants will undergo HE clamp. All patients will have visit 4A.

Visit 4B: The effect of the HFHC meal will be investigated in 24 subjects who participated in visit 1B. Fat biopsy will be done before and after the meal.

Visits 4A and 4B will be separated by 2-5 days.

Compliance

The study coordinator will maintain a log of the entire study drug dispensed and returned.

Storage conditions: stored at room temperature in a locked cabinet.

Drug accountability: A master drug accountability log will be completed on arrival of supplies, Patient specific drug tracking logs will be completed including the following information: Date and amount of drug dispensed, initials of person dispensing study drug, date and amount of drug returned initials of

person receiving returned study drug.

Meal Challenge description

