6. **Plasma glucose, insulin and FFAs measurements:** Insulin levels are determined using an ELISA kit from Diagnostic Systems Laboratories Inc. (Webster, TX). Glucose levels are measured in plasma by YSI 2300 STAT Plus glucose analyzer (Yellow Springs, Ohio). FFAs levels are measured by a colorimetric assay (Roche, Richmond, VA) Active GLP-1 will be measured using ELISA kit (Millipore, MA) from samples collected in DPP-IV inhibitor (Millipore, MA) to prevent GLP-1 degradation. GLP-1 assay sensitivity is 1.5pM.
7. **15-isoprostane F₂t** (also known as 8-epi-PGF2 α or 8-iso-PGF2 α) in urine samples and TBARS will be measured by an ELISA kit from Oxford Biomedical Research (Oxford, MI).
8. **Plasma concentrations of inflammatory cytokines:** Concentrations of IL-6 and TNF α are measured in plasma using sensitive and high sensitive ELISA kits (R&D Systems, MN). ELISA will be used to measure C-reactive protein (American Diagnostica Inc., CT) and DPPIV activity (reported as relative fluorescence units/sec (RFU/sec).
9. **Measurement of whole body glucose uptake and endogenous glucose production by HE clamp:** Subjects will come to the clinical research center after an overnight 10 hour fast. The patient's blood sugar before the clamp is started should be \leq 10mmol/L. Patients with blood sugar $>$ 10mmol/l will be re-scheduled. Oral hypoglycemic medications will be held on the morning of HE clamp. Long acting insulin will be held the night before the clamp. HE clamp will be done using radioactive glucose (3-³H-glucose) as previously described (65, 66). Subjects will arrive at 8 AM for HE clamp with a prime-continuous infusion of 3-³H-glucose. The 3-³H glucose prime will be 20 µCi x (fasting plasma glucose/100); the continuous infusion will be given at the rate of 0.20 µCi/min for 420 minutes (180 minutes for isotopic equilibration and 240 minutes during the insulin clamp). Insulin clamp will be started at 180 min with a priming dose of short acting human insulin given over 10 minutes and then

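### The eligibility and screening text has no pregnancy or breastfeeding criterion or check, although every patient has two radioactive-tracer clamps and the active arm takes linagliptin for 12 weeks

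*Combined protocol and SAP*

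**What the plan says.** All references are to the combined protocol and SAP.

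- **Who may enter.** Study Population plans for "Forty type 2 diabetic patients in the age group of" 20 to 80. The Inclusion Criteria repeat the limit as "Age 20-80 years inclusive" and add type 2 diabetes, a BMI floor, an HbA1c ceiling and stable background medication. Neither place restricts sex.
- **Who is kept out.** The Exclusion Criteria are specific on incretin therapy, pancreatitis and its risk factors, and on coronary, hepatic, renal, blood-pressure and heart-failure limits. The nearest catch-all is "Any other life-threatening, non-cardiac disease". The list closes with "Participation in any other concurrent clinical trial".
- **Screening.** Screening Day consists of history, physical examination, consent and "Baseline lab draws to measure CBC, SMA, lipid profile, fructosamine and HbA1C".
- **Exposure.** Laboratory Procedures, item 9, says "HE clamp will be done using radioactive glucose". Visit 1A includes a clamp and applies to all patients. For week 12 the text reads "The participants will undergo HE clamp. All patients will have visit 4A". On treatment, Study Design says "The first group will be started on 5 mg linagliptin" daily for 12 weeks. The other group takes placebo.

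**The concern.** The eligibility list is the written rule that decides who is enrolled. With a lower age limit of 20 and no restriction on sex, women who could be pregnant or breastfeeding fall within the target population. The list does not address them.

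The tracer is there to measure glucose disposal and endogenous glucose production (Aims 3.1 and 3.2). The plan describes no treatment benefit from it. It reaches both arms, and it is given twice, with a gap long enough for a pregnancy to begin in between. The active arm is also exposed to the study drug during that gap.

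What is at stake is participant protection. Sample size, power, type I error and the JNK-1 analysis are not affected.

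**Working it through.** **Step 1. Is there a criterion or check anywhere in the visible text?**

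| Place | What it covers | Pregnancy or breastfeeding? |
|---|---|---|
| Inclusion Criteria | age, diabetes, BMI, HbA1c, stable medication | not mentioned |
| Exclusion Criteria | from incretin therapy to concurrent trials, printed without a break | not mentioned |
| Screening Day | history, examination, consent, five blood items | no test or status check |
| Visits 1A to 4B | clamps, meals, blood, urine, glucose records | no test or status check |
| Laboratory Procedures, item 9 | before a clamp, blood sugar must be at most 10 mmol/L | no test or status check |
| Assessment of adverse events | birth defects count as serious events | no rule to detect or report a pregnancy |

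The catch-all exclusion concerns life-threatening disease, so it does not reach pregnancy or breastfeeding.

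**Step 2. How far apart are the two tracer exposures?**

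- Patients not taking part in Visits 1B and 1C (40 − 24 = 16) start treatment at the end of Visit 1A, which is their week 0. Visit 4A is at week 12, so the gap is 12 weeks.
- The 24 patients who attend 1B and 1C start treatment at 1C. Visits A, B and C are one week apart, so 1C falls 2 weeks after 1A. The gap is 2 + 12 = 14 weeks.

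**Step 3. How much activity is infused?** The inputs are in Laboratory Procedures, item 9.

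- Continuous infusion: 0.20 µCi/min × (180 + 240) min = 0.20 × 420 = 84 µCi.
- Prime: 20 µCi × (fasting plasma glucose / 100). The formula gives no glucose unit. I assume mg/dL and a range of 70 to 180. The upper end corresponds to the 10 mmol/L limit above which a clamp is rescheduled. The lower end is my assumption.
  - At 70: 20 × 0.70 = 14 µCi.
  - At 180: 20 × 1.80 = 36 µCi.
- Per clamp: 84 + 14 = 98 to 84 + 36 = 120 µCi.
- Two clamps: 2 × 98 = 196 to 2 × 120 = 240 µCi.

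If the formula were meant in mmol/L, the prime at the limit would be 20 × (10/100) = 2 µCi and the total at most 86 µCi per clamp. Either way the 84 µCi infusion is the larger part, and the conclusion does not depend on the unit.

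The plan states no total activity to compare with these figures.

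**The case against.** Four points can fairly be made for the plan.

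1. **Silence is not permission.** A reader might infer that the trial would enrol pregnant women. The documents do not support that. History, examination and consent all precede participation, and a known pregnancy could come up at any of them. This stands. The finding is that no written criterion bars entry, and it does not predict site practice.
2. **Part of the file is not visible.** Consent pages are not in the public copy and could carry a pregnancy warning or a contraception agreement. It would be wrong to say that the study offers no protection. This also stands, but a consent warning is neither an eligibility criterion nor a status check, and the sections that hold those are printed in full.
3. **Activity is not harm.** A reader might take 196 to 240 µCi as a measure of fetal risk. The documents give no absorbed or fetal dose, no risk threshold, no reproductive data on linagliptin and no count of women of childbearing potential. The figures describe what is infused and nothing more.
4. **Two questions are involved.** An exclusion criterion acts at entry and cannot address a later pregnancy, which calls for a check before the second clamp. Drug exposure also applies to one arm only, since the other takes placebo. Both distinctions are right and are kept here.

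None of these points supplies the missing criterion or check.

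**Conclusion.** The point holds as a gap in the written eligibility and screening rules. Followed exactly, they let no one be turned away for pregnancy or breastfeeding, and they contain no step that would detect a pregnancy arising in the 12 to 14 weeks between clamps.

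The exposure that the gap leaves open is 98 to 120 µCi of tracer per clamp and 196 to 240 µCi in total, in either arm, plus 12 weeks of linagliptin in the active arm. The tracer range assumes mg/dL and fasting glucose of 70 to 180. How many participants could be affected is unknown.

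The documents do not support the stronger conclusions that pregnant women would in practice be enrolled, that the study as a whole lacks safeguards, or that a particular degree of harm would follow. The trial's statistical conclusions are untouched.

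**What to change.** Add pregnancy and breastfeeding to the Exclusion Criteria. Have the Screening Day, Visit 1A and Visit 4A procedures confirm status, so that both tracer exposures are covered and not only entry. The exact wording, the method of checking and its timing are for the sponsor and the ethics and radiation reviewers to set. If the consent form already addresses pregnancy, the protocol text should be made to agree with it.

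The cost is a line in the eligibility list and a routine check at visits that already take place. Each visit already includes a blood draw, so no extra visit is needed. Some otherwise eligible patients would be lost. Their number is probably small, but the documents give no figure from which to estimate it.

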Figure 3: Change in CRP (A), FFA (B) and IL-6 (C) concentrations following placebo and Sitagliptin 100mg daily for 12 weeks in type 2 diabetic subjects. N=12 each, data are presented as mean \pm SE. (*, **: $P<0.05$ by RMANOVA (compared to baseline) in sitagliptin and placebo groups, respectively, #: $P<0.05$ by Two-way RMANOVA compared to control groups.)

[figure not shown]

Figure 4: Representative Western blot and percent change in protein levels of JNK-1 after 12 wk of placebo and sitagliptin (100 mg/d) treatment in MNC of obese type 2 diabetic subjects (n = 10 and 12, respectively). Data are presented as mean \pm SE. *, $P < 0.05$ by RMANOVA (compared with baseline); #, $P < 0.05$ by two-way RMANOVA compared with placebo groups.

Study Hypothesis and Aims

Hypothesis 1: Linagliptin treatment suppresses basal and meal induced oxidative and inflammatory stress in mononuclear cells (MNC) and adipose tissue of obese patients with type 2 diabetes.

Aim 1.1: To compare reactive oxygen species (ROS) generation by MNC, protein expression of p47^{phox} subunit of NADPH oxidase, in MNC's and adipose tissue prior to and following 12 weeks of linagliptin or placebo.

Aim 1.2: To compare intranuclear NF κ B binding and the expression of JNK-1, TLR-4, TLR-2, CD26 and TNF α in mononuclear cells (MNC) and adipose tissue before and following 12 weeks of treatment with linagliptin or placebo.

Aim 1.3: To compare plasma hs-CRP and IL-6 concentrations and oxidized lipids in plasma (TBARS) and in urine (F₂-isoprostane) of obese type 2 diabetic patients prior to and following 12 weeks of linagliptin or placebo.

Aim 1.4: To compare post prandial (after a HFHC meal) changes in ROS generation, NF κ B binding and the expression of JNK-1, TLR4, TLR-2 IL-1 β and TNF α in MNC and adipose tissue prior to and following 12 weeks of linagliptin and placebo.

Hypothesis 2: Linagliptin **acutely** suppresses oxidative and inflammatory stress in mononuclear cells (MNC) of obese patients with type 2 diabetes.

Aim 2.1: to study the effect of single dose of linagliptin or placebo on oxidative stress and inflammatory mediators listed in Aim 1.1, 1.2 and 1.3 in MNC from obese type 2 diabetic patients.

Hypothesis 3: Linagliptin is an insulin sensitizer

Aim 3.1: To compare the glucose uptake induced by hyperinsulinemic-euglycemic (HE) clamp prior to and following 12 weeks of linagliptin or placebo.

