2. **ROS generation measurement by chemiluminescence:** Five hundred μ L of MNC (2×10^5 cells) are delivered into a Chronolog LumiAggregometer cuvette. Luminol is then added, followed by 1.0 μ L of 10 mM formylmethionyl leucinyl phenylalanine (fMLP). Chemiluminescence is recorded for 15 minutes. Our method, developed independently(62, 63), is similar to that published by Tosi and Hamedani (64). In this assay system, the release of superoxide radical as measured by chemiluminescence, has been shown to be linearly correlated with that measured by the ferricytochrome C method. The interassay coefficient of variation of this assay is 8 %. We have further established that the biological variation in reactive oxygen species generation in normal subjects is approximately 6 % for readings obtained 1 to 2 weeks apart. Similarly, the variation in reactive oxygen species generation in the obese over a period of 1 to 2 weeks is less than 8 %.
3. **Quantification of IKK β , JNK-1, TNF α , IL-6, IL-1 β , TLR4, TLR2, SOCS-3, PTP-1B, CCR-2 and CD-26 Expression:** The mRNA expression is measured in MNC and adipose tissue by RT-PCR: Total RNA was isolated using commercially available RNAqueous®-4PCR Kit (Ambion, Austin, TX). One μ g of total RNA is reverse transcribed using Advantage RT-for-PCR Kit (Clontech, CA). Real Time RT-PCR was performed using Stratagene Mx3000P QPCR System (La Jolla, CA), Sybergreen master mix (Qiagen, CA) and gene specific primers ([name]).The specificity and the size of the PCR products are tested by adding a melt curve at the end of the amplifications and by running it on a 2% agarose gel. All values were normalized to the expression of a group of housekeeping genes including actin, ubiquitin C and cyclophilin A.
4. **Western blotting:** MNC and adipose tissue total cell lysates are prepared by suspending the cells in 150 μ L of lysis buffer (10 mM Tris-HCl, 150mM NaCl, 0.2 % Triton X and proteases and phosphatases

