an infusion at the rate of 80mU/m². 20% glucose infused through the cephalic vein will be started at 5 minutes and glucose infusion rate will be titrated to maintain blood glucose concentration at the fasting glucose level in the obese and at 5.5mmol/l in T2D. Plasma samples for titrated glucose will be obtained at 10 minute intervals starting 30 minutes before the clamp, to quantitate rates of whole body glucose disposal and suppression of endogenous (primarily hepatic) glucose production. Blood sample will be collected for insulin and free fatty acids (FFA) concentrations every 30 minutes during the clamp. Calculations will be done using Steele's equation(67).

Calculations: Under steady-state postabsorptive conditions, the rate of endogenous glucose appearance (Ra) will be calculated as the $3[{}^3\text{H}]$ glucose infusion rate (disintegrations per minute per minute) divided by the steady-state plasma $3[{}^3\text{H}]$ glucose-specific activity (disintegrations per minute per milligram). During the euglycemic insulin clamp, the rate of Ra will be calculated using Steele's equation, using a distribution volume of 250 ml/kg. Endogenous (primarily hepatic) glucose production (EGP) will be calculated by subtracting the mean exogenous glucose infusion rate during the last 60 minutes (after steady state has been achieved) from Ra. The rate of insulin-mediated total body glucose disposal (Rd) will be determined by adding the rate of residual EGP to the exogenous glucose infusion rate. Insulin sensitivity will be expressed as Rd/lean body mass.

10. **Fat aspiration procedure:** Subjects who are taking antiplatelet or anticoagulant medications will be excluded from the fat biopsy portion of the study. Subcutaneous fat tissue aspiration will be performed on abdomen at a 10 cm distance from umbilicus. The skin will first be prepared and a sterile drape will be placed around the appropriate area. Under local anesthesia, 500mg-3g of fat tissue will be obtained. The adipose tissue will be centrifuged to remove blood and fluid contaminants. The upper adipose tissue will be collected into a separate sterile tube, washed twice with cold sterile Phosphate Buffered Saline (PBS) and centrifuged to remove the PBS. Total RNA, nuclear extracts and total cell lysates will be prepared from the adipose tissue.

DATA ANALYSIS

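### Does the clamp procedure give every participant two conflicting glucose targets?

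*Combined protocol and SAP*

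**What the plan says.** LABORATORY PROCEDURES, item 9, describes the clamp. Glucose infusion is "titrated to maintain blood glucose concentration at the fasting glucose level in the obese and at 5.5mmol/l in T2D". The same item makes a pre-clamp glucose of up to 10 mmol/l acceptable ("Patients with blood sugar $>$ 10mmol/l will be re-scheduled") and refers to two cited methods papers ("as previously described (65, 66").

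STUDY POPULATION enrols one kind of patient: "Forty type 2 diabetic patients in the age group of" 20 to 80 years. INCLUSION CRITERIA adds a BMI of at least 30 kg/m² and an HbA1c of at most 7.5%. There are two arms and no other group: "They will be randomized into 2 groups: placebo and 5 mg/day linagliptin for 12 weeks". Hypothesis 1 names the population by both labels together, as in "adipose tissue of obese patients with type 2 diabetes".

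Under STUDY PROCEDURES BY VISIT, all participants are clamped at Visit 1A and again at Visit 4A. The clamp supplies Aims 3.1 and 3.2 and secondary endpoint (d) in DATA ANALYSIS. The primary endpoint is the change in JNK-1 protein in mononuclear cells.

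**The concern.** The rule assigns a target by label, and every participant carries both labels. Nothing in the documents says that the first label applies to nobody here, or which clause takes precedence.

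The two targets would also make different experiments. A fixed target is the same at baseline and week 12. A target tied to fasting glucose moves when fasting glucose moves. The protocol gives some reason to expect that by arm: the rationale says linagliptin improves glycaemic control, and change in HbA1c is a planned covariate. If the fasting-level clause were applied to these patients, or if operators differed, insulin sensitivity could be compared between visits or arms under unequal clamp conditions. The target also governs the glucose infusion rate, which enters the calculations: endogenous glucose production "will be calculated by subtracting the mean exogenous glucose infusion rate during the last 60 minutes" from the rate of appearance.

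**Working it through.** **1. How many clamps the wording touches.** By the inclusion criteria, all 40 participants meet both labels. Two clamps each gives 40 × 2 = 80. With the planned loss of 3 per group, (20 − 3) × 2 = 34 paired completers, or 68 clamps. These counts show how far the wording reaches. They do not measure error.

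**2. How far apart the targets are.** Gap = fasting glucose − 5.5 mmol/l. The documents give no fasting-glucose distribution, so the fasting values are assumptions.

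| Assumed fasting glucose (mmol/l) | Gap (mmol/l) | Gap as % of 5.5 |
|---|---|---|
| 5.5 | 0 | 0 |
| 6 | 0.5 | 9 |
| 7 | 1.5 | 27 |
| 8 | 2.5 | 45 |

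At the 10 mmol/l start limit the gap is 4.5 mmol/l. That is an arithmetic bound, not an expected value. For an assumed change in fasting glucose of 0.5 or 1.0 mmol/l between visits, a fasting-tied target moves by the same amount and a fixed target by 0.

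**3. Whether the gap becomes a bias in the endpoint.** Write Ra for the rate of glucose appearance, GIR for the mean exogenous glucose infusion rate, EGP for endogenous glucose production and Rd for glucose disposal. Item 9 gives EGP = Ra − GIR and Rd = EGP + GIR. With the same mean GIR in both, Rd = Ra. The formulas give neither the size nor the direction of any effect of the target on Rd. Scaling Rd in proportion to glucose would need constant glucose clearance, which the documents do not state.

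**4. What the two labels mean in this document.**
- In item 9 the labels stand in contrast: one rule for one set of people, another rule for another. If both named the same people, the sentence would give two targets for one clamp.
- Elsewhere the bare term 'the obese' is a general category. Item 2 of the same section reports "the variation in reactive oxygen species generation in the obese over a period of 1 to 2 weeks" after giving the figure for normal subjects. The background sets caloric restriction in the obese beside fasting in normal subjects, and the section on insulin sensitization says SOCS-3 expression is raised in the obese. None of these means the trial's participants.
- When the hypotheses and aims mean the participants, they join the labels: obese patients with type 2 diabetes, or obese type 2 diabetic patients.
- The clamp is called euglycemic in the background, in Aim 3.1 and in item 9.

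Read together, the first clause describes a group that was not enrolled, and the second covers all 40 patients. That yields one target, the same at Visits 1A and 4A and in both arms.

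**The case for a change.** The strongest reply is that this answer is inferred. No sentence says the first clause is void. The uses of 'the obese' elsewhere that carry a contrast set it against normal subjects, not against people with diabetes, and the hypotheses call these diabetic participants obese. The cited clamp methods cannot be consulted here; the title of one names type 2 diabetic patients, but that does not show which target it used. A clarifying sentence would cost almost nothing.

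It stands that the wording is untidy and the resolution is not explicit. It also stands that a target tied to fasting glucose would raise a real question of comparability between visits. That question depends on staff setting aside the clause that names the trial's own diagnosis. Nothing in the documents suggests they would, or that they would switch rules between visits or arms: the trial is double-blind, at one named centre, with one written procedure for both arms. Reporting achieved clamp glucose by arm and visit would be reasonable, but it is optional and repairs no error in the plan.

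**Conclusion.** The two labels overlap in this population, so the observation about the text is correct. It is a clerical leftover in the procedure for a secondary endpoint. On the ordinary reading, all participants fall under one clause and are clamped to one fixed target at both visits in both arms. Rewording would therefore not alter what the trial does or concludes. No effect on Rd or endogenous glucose production can be derived from the documents, and the primary endpoint and sample size do not depend on the clamp.

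The conclusion rests on reading the contrast in item 9 as one between different people, which the document's usage supports but does not state. The 0.5 to 2.5 mmol/l gaps rest on assumed fasting values. If the protocol is revised for another reason, item 9 can be reconciled with STUDY POPULATION in passing; the choice of target belongs to the sponsor and the investigator.
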